**V. STUDY PROCEDURE**

**a. Overall Research Design and Methods**

This study has been split into two parts. **Part 1 is the initial randomized control trial, and Part 2 is when the participants can select the treatment they want to receive if they are not satisfied with their initial treatment.** In Part 1 patients will not be blinded to the treatment arm that they receive due to the obvious differences in the treatments.

Participants will also be asked to log their return to running at home using the University of Delaware Return to Sport protocol.

*Part 1*

Study participants will be randomly assigned to one of three treatment groups, using a block randomization generator **that is implemented into REDCap**. There will be 20 patients per treatment group, no power calculation as this is a feasibility study. The three treatment arms are: physical therapy only, SWT and physical therapy, and a combination of SWT, PBMT and physical therapy. All runners, regardless of treatment group, will be asked to enroll in physical therapy at a location that is convenient to them (and accepts their insurance if applicable) and complete a standard physical therapy program addressing individual strength deficits in both proximal (spine and hip girdle) along with distal (thigh, leg and foot/ankle) muscle groups. To standardize loading program, we will provide all runners with an at-home exercise program designed by [name] for progressive Achilles tendon loading. This will be

completed alongside the physical therapy they are receiving. Activities including running will be allowed as tolerated following published guidelines by [name].

In subjects who have bilateral AT, the leg with the most severe symptoms (determined by the VISA-A) will be chosen as the primary data for the study, however both legs will be treated consistent with the treatment group the subject was randomized into. Outcomes will be obtained for each Achilles tendon, regardless of treatment, using VISA-A at each data collection point. Participants will also be asked to complete a weekly log of running and completing PT exercises.

## Part 2

At the 3-month follow-up, participants who are not satisfied with their outcome will be given the option to choose one of the remaining treatment arms. Regardless of what treatment a patient chooses, if any, there will be one final visit conducted at 6 months for final data collection.

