**b. Visit Details**

After consent has been obtained, patients will be randomly allocated to one of the three treatment arms. The expectations for the visits for the different study arms are outlined below:

Table 1: Outlined visits from three different study arms

	Physical Therapy only	Shockwave	PBMT & Shockwave
T0: Baseline	Subject screening & enrollment*		
Part 1	Subject to be randomly assigned a treatment arm		

T1: week 1 visit 1	VISA-A, ProMIS-29, UWRI, patient goals Ultrasound, heel raises & hopping test	Treatment 1 VISA-A, ProMIS-29, UWRI, patient goals Ultrasound, heel raises & hopping test	PBMT & SW treatment VISA-A, ProMIS-29, UWRI, patient goals Ultrasound, heel raises & hopping test
T2: week 1 visit 2	telephone check-in	telephone check-in	PBMT treatment only
T3: week 2 visit 1	telephone check-in	Treatment 2	PBMT & SW treatment
T4: week 2 visit 2	telephone check-in	Telephone check-in	PBMT treatment only
T5: week 3 visit 1	telephone check-in	Treatment 3	PBMT & SW treatment
T6: week 3 visit 2	telephone check-in VISA-A, ProMIS-29, UWRI	telephone check-in VISA-A, ProMIS-29, UWRI	PBMT treatment only VISA-A, ProMIS-29, UWRI
T7: 6 week follow up	telephone check-in VISA-A, ProMIS-29 & UWRI	telephone check-in VISA-A, ProMIS029 & UWRI	telephone check-in VISA-A, ProMIS-29 & UWRI
T8: 3 month follow up	VISA-A, ProMIS-29, UWRI, patient goals, patient satisfaction, new treatment selection Ultrasound, heel raise & hopping test	VISA-A, ProMIS-29, UWRI, patient goals, patient satisfaction, new treatment selection Ultrasound, heel raise & hopping test	VISA-A, ProMIS-29, UWRI, patient goals, patient satisfaction, new treatment selection Ultrasound, heel raise & hopping test
Part 2	Participants to choose treatment and follow visit schedule as listed above		
T9: 6 month follow up	Patient satisfaction, ultrasound, heel raises & hopping test	Patient satisfaction, ultrasound, heel raises & hopping test	Patient satisfaction, ultrasound, heel raises & hopping test

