### **c. Statistical methods**

For the statistical analysis of both the primary outcome, VISA-A, and secondary outcomes, PROMIS-29, UWRI, VAS, ultrasound measurements, and functional tests, we will use the

Shapiro-Wilk test to for normality in the data. For the continuous data we will use the t-test and ANOVA test if the data is normally distributed, and we will use the Mann-Whitney U test and Kruskal-Wallis analyze the data that is not normally distributed. For the binary data we will use the chi or Fishers test to compare the data.

In the first phase of the study, the randomized control trial, we will use a multivariable linear regression, controlling for: sex, BMI, age, medical condition (thyroid disease and diabetes) and prior oral steroid and/or fluoroquinolone use. In phase 2 after the elective cross-over, we will use the models described above as repeated measure models.

Interim analysis will be performed after 30 participants are enrolled to review for safety and tolerance to treatment.

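### Part 1 analysis of VISA-A names no time point, repeated-measures structure or missing-data method, so as written a participant who misses month 3 adds nothing to the 3-month comparison

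*Combined protocol and SAP*

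**What the plan says.** Section VI.c makes VISA-A the primary outcome. It offers t-test/ANOVA or rank tests for continuous data ("For the continuous data we will use the t-test and ANOVA test if the data is normally distributed") and then gives the model for the randomised phase: "In the first phase of the study, the randomized control trial, we will use a multivariable linear regression". The adjustment terms are demographic and medical; neither visit nor baseline VISA-A is among them. The next sentence turns to the later phase: "In phase 2 after the elective cross-over, we will use the models described above as repeated measure models".

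The schedule is richer than the model. Table 1 (V.b Visit Details) has VISA-A at the third-week contact ("telephone check-in VISA-A, ProMIS-29, UWRI" for the two arms with a call at that point, and the same questionnaires in the combined arm), at 6 weeks and at 3 months. Table 2 repeats this for all arms. Section V.a adds: "Outcomes will be obtained for each Achilles tendon, regardless of treatment, using VISA-A at each data collection point". A new treatment may be chosen only at the 3-month visit, so all three post-baseline scores belong to the randomised comparison.

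No section names a Part 1 time point, an analysis set or a way of handling missing scores. The Compensation text foresees early withdrawal.

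**The concern.** An ordinary linear regression takes one outcome value per participant and omits anyone without it. Section VI.c names repeated-measures models in the very next sentence, for phase 2 only, so the natural reading is that Part 1 does not use them. Someone who gave VISA-A at 3 and 6 weeks and then missed month 3 would drop out of the 3-month comparison, although the 6-week score is the best available predictor of the missing value.

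Participants know their arm, and during weeks 1 to 3 the physical-therapy-only arm receives calls where the other arms attend for treatment. Loss that depends on arm and early response is therefore plausible. With 20 per arm, a few selective losses can move the estimate. Section II states the primary aim as evaluating effects between arms, so the quality of that estimate matters even in a pilot.

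**Working it through.** **1. The plan's own figures.** 3 arms × 20 = 60, which agrees with section IV.a. The plan gives no power, alpha, SD, effect size or loss rate, so there is nothing further to reproduce. Every rate, SD and correlation below is an assumption.

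**2. Possible readings of the Part 1 regression.**
- One visit (3 months): those who miss it are omitted.
- A separate regression or test at each visit: those who miss month 3 are still omitted from the 3-month result, and there are several looks with no primary one.
- All visits pooled in an ordinary regression: correlated scores are treated as independent.

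Under the first two, early scores do not inform a missing 3-month value. The third is not a valid analysis.

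**3. Precision if loss is random.** Let q be the share observed at 3 months and R² the share of 3-month variance explained by the earlier scores. Relative to full data, the variance is 1/q for complete cases and (1 − R²)/q + R² for a likelihood-based repeated-measures model. Effective n per arm is 20 divided by that factor. For 20% missing and R² = 0.5, the complete-case n is 20 × 0.8 = 16. The model factor is 0.5/0.8 + 0.5 = 1.125, so effective n is 20/1.125 = 17.8.

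| Missing at 3 months | Complete-case n per arm | Effective n, R² = 0.3 / 0.5 / 0.7 | Reduction in SE |
|---|---|---|---|
| 10% | 18 | 18.6 / 18.9 / 19.4 | 1.5 / 2.5 / 3.6% |
| 20% | 16 | 17.0 / 17.8 / 18.6 | 3.0 / 5.1 / 7.3% |
| 30% | 14 | 15.4 / 16.5 / 17.7 | 4.6 / 7.8 / 11.1% |

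**4. Bias in VISA-A points.** Simulation of 6,000 trials with two arms of 20. Assumed SDs are 13, 15, 16 and 17 at baseline, 3 weeks, 6 weeks and 3 months; the 6-week to 3-month correlation is 0.8; the true 3-month difference is 8. The comparison is a 3-month regression on arm and baseline in completers against the likelihood estimate that also uses the 3- and 6-week scores.

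| Loss pattern | Completers: bias (SD) | Likelihood: bias (SD) |
|---|---|---|
| 15% loss; poor early responders in the physical-therapy-only arm leave more often (35% v 5%) | −1.58 (5.31) | 0.01 (5.09) |
| 20% loss, opposite selection in the two arms | −3.22 (5.55) | 0.01 (5.30) |
| 15% random | none (5.21) | none (5.01) |
| 20% random | none (5.51) | none (5.15) |

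As shares of the assumed effect, 1.58/8 = 20% and 3.22/8 = 40%. Variance under random loss falls by 1 − (5.01/5.21)² = 7.5% at 15% loss and by 1 − (5.15/5.51)² = 12.6% at 20% loss.

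Variations on these assumptions:
- Good responders in the physical-therapy-only arm leave instead: completer bias +1.5.
- Correlation 0.5 instead of 0.8: completer bias −0.9 and −1.9 in the two selective patterns, and a variance gain under random loss of only 1 to 2%.
- The same selection rule in both arms (30% v 5%, about 16% loss): completer bias −0.2, about zero.
- Loss in the physical-therapy-only arm depends on the unobserved 3-month score: −1.9 for completers and −0.8 for the likelihood estimate.

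**5. The same check in SD units.** 5,000 trials, 20 per arm, true difference 0.5 SD, poor 6-week responders missing month 3; here the completer estimate is a plain difference in means. With 20% missing in each arm, completers give 0.51 and 0.50 at correlations 0.5 and 0.7, so no bias. With 10% missing in one arm and 30% in the other, they give 0.38 and 0.33; the repeated-measures approach gives 0.50 at both.

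**The case against.** **The plan does not say this.** A reader might infer that the plan prescribes a single-visit, 3-month regression, excludes anyone who misses that visit and discards the 3- and 6-week scores. The documents do not support that as a stated rule. Section VI.c names no visit. The early scores could be tested separately, and the phase 2 repeated-measures models could include them. This stands, and the point is limited to what the wording implies. It does not rescue the 3-month contrast, because no workable reading lets early scores inform a missing 3-month one.

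**Bias is not inevitable.** Loss that depends on the 6-week score is not enough; the dependence must differ by arm. The design also gives dissatisfied runners in the physical-therapy-only arm a reason to attend month 3: they may choose another arm, PBMT or SWT is free, a $50 payment is attached, and visits may move by 14 days either way. All of this stands. Neither the size nor the direction of any bias is established.

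**The better model is not immune.** It removes the bias only when loss depends on observed scores. The simulations also simplify: two arms, a closed-form estimator, complete early scores, and a points-scale comparator that adjusts for baseline VISA-A, which the plan does not list, and omits the planned covariates. The ±14-day allowance lets the 3-week window (to 3 + 2 = week 5) overlap the 6-week window (from 6 − 2 = week 4), which blurs visit-specific terms. These are fair limits on the figures. None makes the completer regression preferable.

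**It is a pilot.** No power is claimed, so lost precision carries little weight. Bias in the estimate still does.

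**Conclusion.** The concern holds in a limited form. The Part 1 analysis names no time point and no missing-data method, and repeated-measures models are mentioned only for phase 2. As written it implies complete-case analysis at each visit tested, which leaves early scores unused for anyone missing month 3.

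If loss depends on early response differently by arm, the 3-month difference is off by about 1.5 to 3 points on an assumed true 8, with either sign possible, at an assumed correlation of 0.8; at 0.5 it is about 0.9 to 1.9. Set against an SD of the estimate of about 5.3 to 5.6, that is 1.58/5.31 = 0.3 to 3.22/5.55 = 0.6 of an SD. With the same selection in each arm the bias is about zero. With random loss the gain is only precision: about 7 to 8% of variance at 15% loss and correlation 0.8, less at lower correlation.

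A reader should not conclude that the trial's result will be biased, or in which direction: the documents give no loss rate and no pattern of loss. This is a worthwhile, inexpensive improvement using data already scheduled.

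**What to change.** In section VI.c:

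- Name 3 months as the Part 1 time point for VISA-A.
- Replace the Part 1 regression with one mixed model for repeated measures on the 3-week, 6-week and 3-month VISA-A scores, and do likewise for UWRI and PROMIS-29.
- Include, as randomised, all participants with at least one post-baseline score. Someone with none adds nothing to this model, and the plan should say so.
- Use arm, visit, arm-by-visit, the baseline score of the outcome, baseline-by-visit and the covariates already planned, with unstructured covariance and small-sample degrees of freedom. Read the arm contrasts at 3 months.
- State that the analysis is valid when loss depends on observed scores, and add one sensitivity analysis that shifts the missing 3-month scores by arm.

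The cost is wording and a little programming, with no new visits, data or participants. The downside is a few more covariance parameters in a 60-person dataset.

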## III. SUBJECT SELECTION

### a. Inclusion/Exclusion Criteria

#### Inclusion Criteria

Patients will be eligible if they meet the following criteria:

- Patients aged between 18-65 years old with a diagnosis of mid-portion Achilles tendinopathy (including both unilateral and bilateral)
- Running is the pre-injury primary form of physical activity and pre-injury would complete on average 10 miles per week or more of running
- VISA-A <80 at baseline to be eligible

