### **Study Visits for all treatment arms:**

An overview of the questionnaires and measurements that will be taken at various time points, regardless of treatment arm, are described in table 2.

Table 2: Overview of questionnaires and measurements required regardless of treatment arm

Visit	Questionnaires							Measurements	
	VISA-A	ProMIS-29	UWRI	Patient goals	Treatment preference	Patient satisfaction	Return to sports worksheet collection	Ultrasound	Heel raise & hopping test
Baseline	x	x	x	x	x			x	x
3-week follow-up	x	x	x				x		
6-week follow up	x	x	x				x		
3-month follow-up	x	x	x	x	x	x	x	x	x
6-month follow up	x	x	x	x	x	x	x	x	x

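### The Part 1 regression does not adjust for baseline VISA-A, which every participant has, and the plan leaves the 3-month primary visit and the outcome form (value or change) unstated.

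*Combined protocol and SAP*

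**What the plan says.** Section VI.c names the outcomes without a visit or a scale: "For the statistical analysis of both the primary outcome, VISA-A, and secondary outcomes, PROMIS-29, UWRI, VAS, ultrasound measurements, and functional tests". It then gives simple tests: "For the continuous data we will use the t-test and ANOVA test if the data is normally distributed", with Mann-Whitney and Kruskal-Wallis otherwise. None of these carries a baseline term. For the randomised phase it adds a "multivariable linear regression, controlling for: sex, BMI, age, medical condition (thyroid disease and diabetes) and prior oral steroid and/or fluoroquinolone use". Repeated-measures versions are mentioned only for the later phase: "In phase 2 after the elective cross-over, we will use the models described above as repeated measure models".

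Baseline VISA-A will exist for everyone:

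- Inclusion Criteria: "VISA-A <80 at baseline to be eligible".
- Section V.a: "Outcomes will be obtained for each Achilles tendon, regardless of treatment, using VISA-A at each data collection point". In bilateral cases, "the leg with the most severe symptoms (determined by the VISA-A) will be chosen as the primary data for the study".
- Table 2 ("Overview of questionnaires and measurements required regardless of treatment arm") marks VISA-A at baseline, 3 weeks, 6 weeks, 3 months and 6 months.

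Section VI.b lists the subjective endpoints only as questionnaires. Section II describes a randomised phase of 3 months and hypothesises improvement relative to baseline. Neither section defines the analysed variable.

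**The concern.** The baseline value of the outcome is usually among the strongest predictors of its follow-up value. Here it is collected on everyone, yet the model spends its degrees of freedom on sex, BMI, age, two medical conditions and prior drug use. Two things are at stake.

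- **Precision.** With 20 per arm, arm differences will have wide intervals, and variance that baseline explains stays in the error term.
- **Chance imbalance.** A difference between arms in starting VISA-A is carried into the estimate. How it is carried depends on whether the value or the change is analysed, and the plan does not say which.

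**Working it through.** The plan has no power, SD or precision figure to reproduce; section V.a says that no power calculation was made.

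**Inputs from the documents.** 60 participants, 20 per arm. The listed model has 9 parameters: intercept, two arm terms, sex, BMI, age, thyroid disease, diabetes and prior drug use (taken as one term). That leaves 60 − 9 = 51 residual degrees of freedom, or 50 with baseline added.

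**Assumed inputs (not in the documents).** Follow-up SD Sf = 18 points; baseline SD Sb = 18, 15 or 12; correlation r = 0.2 to 0.7; no dropout. The VISA-A entry limit truncates the baseline range, so Sb below Sf is plausible, and r may be lowered too.

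**Formulas.** Variance of an arm difference, divided by 2/n:

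- Follow-up value: Sf²
- Change score: Sf² + Sb² − 2·r·Sf·Sb
- ANCOVA: Sf²(1 − r²) × 1.020, where 1.020 = 1 + 1/(51 − 2) charges for estimating the baseline slope

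**Step 1: against the follow-up value.** The net cut is 1 − 1.020(1 − r²). The 95% half-width is t × √(variance × 2/20), with t = 2.008 (51 df) or 2.009 (50 df). Without baseline it is 2.008 × 18 × √0.1 = 11.4 points.

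| r | Net variance cut | Half-width with baseline |
|---|---|---|
| 0.2 | 2% | 11.3 |
| 0.3 | 7% | 11.0 |
| 0.5 | 23% | 10.0 |
| 0.7 | 48% | 8.2 |

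Break-even is where 1.020(1 − r²) = 1, that is r ≈ 0.14. Below that, adjustment costs slightly more than it gains.

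These widths leave out the precision that the other six covariates use up. Simulating the full model, with those covariates as pure noise, gives 12.0 points without baseline and 11.9 / 11.6 / 10.5 / 8.7 with it. The closed-form widths are therefore about 5% too narrow for the listed model; the relative cuts hold.

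**Step 2: against a change score.** Net variance cut from ANCOVA:

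| Baseline SD | r = 0.3 | r = 0.5 | r = 0.7 |
|---|---|---|---|
| 18 | 34% | 23% | 13% |
| 15 | 22% | 11% | 1% |
| 12 | 11% | 2% | −2% |

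Example (Sb = 12, r = 0.7): change 324 + 144 − 302.4 = 165.6; ANCOVA 324 × 0.51 × 1.020 = 168.6; a loss of about 2%.

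**Step 3: chance imbalance.** For one given pair of arms, the chance of a baseline difference above 5 points is 2 × P(Z > 5/(Sb√0.1)) = 19% / 29% / 38% at Sb = 12 / 15 / 18 (normal approximation). With slope b = r·Sf/Sb, a difference D moves the follow-up value by b·D and the change score by (b − 1)·D. For D = 5, Sb = 18 and r = 0.5, that is +2.5 and −2.5 points. The directions are opposite only when b lies between 0 and 1; at Sb = 12 and r = 0.7, b = 1.05 and both shifts are positive (+5.25 and +0.25). Averaged over randomisations the shift is zero.

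**Step 4: value or change.** Subtracting baseline from an outcome whose model already contains baseline lowers the baseline slope by exactly 1 and leaves the arm coefficients unchanged. Once baseline is in the model, the choice between value and change no longer affects the treatment estimate.

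**Step 5: which measurement is baseline.** Table 1 puts screening at T0, then random assignment, then T1. VISA-A, PROMIS-29, UWRI, ultrasound and the functional tests are first listed at T1, which is also the first treatment visit in both shockwave arms. Participants are unblinded. Only the VISA-A used for eligibility is assured to precede allocation.

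**The case against.** **This is a pilot without a power target.** That stands. A reader might infer that the trial misses its power because of this omission, but there is no target to miss. The point concerns the precision and definition of the estimates. The primary aim still compares arms, and section VI.c commits to a regression.

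**Randomisation deals with baseline differences.** On average it does. A reader might infer a biased comparison; the documents do not support that.

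**The endpoint is clear enough.** Largely so. VISA-A has three Part 1 follow-up visits and two possible forms, and a reader might infer six equally open analyses and a risk of picking the best. The 3-month randomised phase, and the choice of a new treatment at its end, point to 3 months; ultrasound and functional tests have only that Part 1 follow-up. This is a gap in wording, not evidence of a free choice.

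**The gain may be nil.** This stands. If change is meant, as the improvement hypothesis in section II suggests, the gain can vanish when baseline SD is small, and against the value it vanishes near r = 0.14. In the scenarios examined, however, the worst loss is about 2% of variance.

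**The remedy does not carry over unchanged to every secondary outcome.** This also stands. On Table 1's schedule, their first measurement follows allocation, and the ultrasound measures in section VI.a include neovessel presence (binary) and number (a count).

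**Conclusion.** The concern holds as a low-cost improvement. Section VI.c omits baseline VISA-A from the Part 1 model, and no section states the primary visit or the outcome form; these are facts of the text. The size of the gain is not. It rests on an assumed SD and correlation and on treating the other covariates as unrelated to VISA-A. On those assumptions it ranges from negligible to about half the variance against the follow-up value, and from a third to slightly below zero against a change score. The likely loss from adjusting is trivial, so the case for adding baseline does not depend on knowing the correlation.

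**What to change.** State the primary Part 1 analysis as an ANCOVA: index-leg VISA-A at 3 months on treatment arm, with the listed covariates plus baseline VISA-A of the same leg. Identify that baseline as the eligibility score, taken before allocation, and record it for each leg in bilateral cases. Describe the unadjusted t-test, ANOVA and rank tests as supportive.

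For the continuous secondary outcomes with a scheduled first measurement (PROMIS-29, UWRI, tendon cross-sectional area and thickness, heel raises, hop-test pain), adjust for that measurement. State that it is taken before the first treatment, and acknowledge that Table 1 places it after allocation. Do not extend linear ANCOVA to neovessel presence or number. Neither visit table schedules the stand-alone pain VAS, so it has no baseline to adjust for.

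Cost: plan wording and one residual degree of freedom (51 to 50). No new assessments are needed.
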